7.6.9. Ophthalmic Examination

Visual Acuity

Visual acuity will be measured using the Snellen visual acuity. This is determined by establishing the smallest optotypes that can be identified correctly by the participant at a given observation distance. Snellen visual acuity can be reported as a Snellen fraction (m/M) in which the numerator (m) indicates the test distance and the denominator (M) indicates the distance at which the gap of the equivalent Landolt ring subtends 1 minute of arc.

For each timepoint, the LogMAR score will be calculated as $-\log(m/M)$.

Total visual acuity score will also be assessed identifying clinically meaningful deterioration in LogMAR. The number of participants reporting a change in score of ≤ 0 , 0 to <0.1, 0.1 to <0.2, 0.2 to <0.3 and ≥ 0.3 LogMAR will be summarized in shift table.

Maximum number of loss lines should be tabulated for post baseline assessment.
The change from baseline will be classified as:

- if change from baseline in terms of logmar is >0.26 then " ≥ 3 line loss";
- if change from baseline in terms of logmar is > 0.16 and ≤ 0.26 then "2 line loss";
- if change from baseline in terms of logmar is ≥ -0.16 and ≤ 0.16 then " ± 1 line loss";
- if change from baseline in terms of logmar is $.<$ and <-0.16 then " >1 line increase".

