| - | 15.00 | 2.00 | -1.18 | 16 | 300 | 90.0 | 0.07 | 0 | 210.0 | 525.0 | - | - | 6.0 |
| 12 | 16.00 | 1.88 | -1.20 | 15 | 320 | 96.0 | 0.06 | 0 | 224.0 | 560.0 | - | - | 6.4 |
| 13 | 20.00 | 1.50 | -1.30 | 10 | 400 | 120.0 | 0.05 | 0 | 280.0 | 700.0 | - | - | 8.0 |
| 16 | 40.00 | 0.75 | -1.60 | 5 | 800 | 240.0 | 0.03 | 0 | 560.0 | 1400.0 | - | - | 16.0 |
| 20 | 100.00 | 0.30 | -2.00 | 0 | 2000" | 600.0 | 0.01 | 0 | 1400.0 | 3500.0 | - | - | 40.0 |
| 30 | 1000.00 | 0.03 | -3.00 | 0 | 200001 | 6000.0 | 0.001 | 0 | 14000.0 | 35000.0 | - | - | 400.0 |

Bold values are standard logMAR progression.

LogMAR = logarithm of the minimum angle of resolution

*20/2000 is equivalent to counting fingers @ 2 feet

120/20000 is equivalent to hand motion @ 2 feet

Holladay J. Visual acuity measurements. J Cataract Refract Surg. 2004;30(2) 297-90.

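### SAP 7.6.9 groups LogMAR change in classes that overlap at 0 and cut at exact tenths, so equal Snellen line losses can land in different classes depending on the starting line

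*SAP*

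**What the plan says.** SAP 7.6.9 plans two tabulations of visual acuity from one score. Acuity is recorded as a Snellen fraction m/M ("Visual acuity will be measured using the Snellen visual acuity"), and "the LogMAR score will be calculated as" minus the log of m/M. The section states neither the base of the logarithm nor how scores or changes are rounded.

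The first tabulation is a shift table of participants "reporting a change in score of ≤ 0 , 0 to <0.1, 0.1 to <0.2, 0.2 to <0.3 and ≥ 0.3 LogMAR". It is introduced as a way to identify deterioration that matters clinically.

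The second tabulates the maximum number of lines lost. It cuts at 0.16 and 0.26. For example, "if change from baseline in terms of logmar is > 0.16 and ≤ 0.26 then" the change counts as two lines lost, and anything above 0.26 counts as three or more. Changes from -0.16 to 0.16 form a single class of plus or minus one line.

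Protocol Appendix 7 supplies the Snellen conversion chart, with LogMAR printed to two decimals and the note "Bold values are standard logMAR progression".

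**The concern.** Two things in the shift table do not work as written. First, "reporting a change in score of ≤ 0" and the class that starts at 0 both contain 0, the value for an unchanged patient. Second, the remaining limits ("0 to <0.1, 0.1 to <0.2, 0.2 to <0.3") sit where a whole number of lines would fall if each line were exactly 0.1 LogMAR. Snellen denominators are rounded, so actual steps scatter narrowly around 0.1, 0.2 and 0.3. A limit placed in the middle of that scatter sorts patients by starting line rather than by how much vision they lost.

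Visual acuity is tested on Day 1 of every cycle (Protocol 7.3.5). Protocol 2.1.4 reports serous retinopathy in 20% of patients on this combination in the melanoma trial, symptomatic in 8%. A reader who takes the ≥0.3 class as three lines or more would miss some three-line losses, and would find the line-loss table giving a different picture of the same patients.

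**Working it through.** **Inputs.** The formula, change classes and line-loss limits come from SAP 7.6.9. The Snellen denominators are the consecutively numbered rows of Protocol Appendix 7 from 20/10 to 20/200: 10, 12.5, 16, 20, 25, 32, 40, 50, 63, 80, 100, 125, 160, 200. Base 10 and unrounded scores are assumed.

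**1. Reproduce the chart.** In size, LogMAR = log10(M/20) for a 20/M reading:
- 20/25: log10(25/20) = 0.0969, printed as 0.10
- 20/32: log10(32/20) = 0.2041, printed as 0.20
- 20/63: log10(63/20) = 0.4983, printed as 0.50
- 20/200: log10(200/20) = 1.0000, printed as 1.00

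All 23 rows from 20/10 to 20/400, including the unnumbered ones, agree with the chart in size to two decimals. The chart prints the opposite sign to the SAP formula (20/200 is -1.00 there and +1.00 by the formula), so this comparison is of magnitude only. The agreement confirms base 10.

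**2. Change for a loss from 20/M1 to 20/M2** = log10(M2/M1).

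| Lines lost | Steps | Range of change | Class most would expect | Steps one class lower |
|---|---|---|---|---|
| 1 | 13 | 0.0969 to 0.1072 | 0.1 to <0.2 | 8 |
| 2 | 12 | 0.1938 to 0.2041 | 0.2 to <0.3 | 4 |
| 3 | 11 | 0.2942 to 0.3010 | ≥0.3 | 2 |

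- One line: 20/20 to 20/25 is 0.0969 (0 to <0.1), but 20/25 to 20/32 is 0.1072 (0.1 to <0.2).
- Two lines: 20/32 to 20/50 is 0.1938 (0.1 to <0.2), but 20/20 to 20/32 is 0.2041 (0.2 to <0.3).
- Three lines: 20/32 to 20/63 is 0.2942 and 20/63 to 20/125 is 0.2976 (both 0.2 to <0.3), but 20/20 to 20/40 is 0.3010 (≥0.3).

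**3. Same steps under the line-loss limits.** The largest one-line step, 0.1072, is below 0.16. All two-line steps (0.1938 to 0.2041) lie between 0.16 and 0.26. The smallest three-line step, 0.2942, is above 0.26. All 13 + 12 + 11 = 36 steps therefore fall under their own label, though the one-line label also takes in no change. A patient going from 20/32 to 20/63 is counted as three or more lines lost in one table and as 0.2 to <0.3 in the other.

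**4. The value 0.** It satisfies change ≤ 0 and also 0 ≤ change < 0.1. The text does not say which class applies.

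**5. Sensitivity of the counts** (one-, two- and three-line steps falling low).
- Rows 20/20 to 20/200 only: 6 of 10, 3 of 9, 2 of 8.
- Rows 20/10 to 20/400: 10 of 16, 5 of 15, 2 of 14. In metre notation: 9, 6 and 3.
- Scores first rounded to two decimals, 20/10 to 20/400: differences are exactly 0.10, 0.20 and 0.30 in decimal arithmetic and none falls low. In ordinary binary floating point 8, 7 and 2 still do.
- Change rounded to two decimals, 20/10 to 20/400: 0, 4 and 1.
- Change rounded to one decimal, 20/10 to 20/400: none.

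**The case against.** The shift table bins a change in score and nowhere says that its classes are line counts. A change of 0.0969 is truly below 0.1, and 0.2942 is truly below 0.3. Lines are counted in the separate table, which gets every two- and three-line loss right, so a large loss is not hidden from the report. Ocular events also appear in the graded adverse event tables. The table shells are in a separate document (SAP section 2) that is not available here and may settle the edges. All of this stands, and it is why the point is minor. It does not resolve the double membership of 0, nor the fact that a table meant to flag meaningful loss sorts equal losses by starting line.

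Stronger readings are tempting but not supported:
- A reader might infer that most one-line losses are tabulated together with unchanged vision. That follows only if 0 is counted in the class from 0 to <0.1, in line with the closed lower limits of the next classes. If 0 is counted in ≤0, no one-line loss shares a class with no change. The text allows either. The line-loss table, by contrast, does pool one-line loss with no change, by design.
- A reader might infer that the table will be run on natural logs, because the SAP names SAS and leaves the base unstated. That would turn 20/20 to 20/25 into ln(25/20) = 0.223 and label it two lines. The Appendix 7 values and the 0.16 and 0.26 limits fit base 10 only, so the missing base is an editorial gap.
- A reader might take the 20% as ocular toxicity in general. It is the serous retinopathy figure.

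**Conclusion.** The point holds as a minor defect of specification. As written, 0 belongs to two classes, and over chart rows 20/10 to 20/200, 8 of 13 one-line, 4 of 12 two-line and 2 of 11 three-line steps fall one class below other losses of the same number of lines. The two tables in the section can therefore disagree for the same patient.

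The counts rest on unrounded base-10 scores in feet notation and on equal weight for each chart step. They should not be read as proportions of patients, because neither document gives a distribution of acuity. They shift with the row range and with any rounding rule. No efficacy result depends on this table, and the primary response analysis is untouched.

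**What to change.** Make the classes mutually exclusive and place the cuts between line steps. Two ways would do it:

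- Use ≤0, >0 to ≤0.16, >0.16 to ≤0.26 and >0.26. The upper limits then match the line-loss table, and the split at 0 separates one-line loss from no change. The price is that limits are no longer round tenths, and partial-line changes such as 20/25 to 20/30 (0.0792) sit with full one-line losses.
- Keep the tenths, write the first positive class as >0 to <0.1, and round the change to one decimal before classing. Partial-line changes then move to the nearest tenth (0.0792 becomes 0.1). The >0 to <0.1 class would be empty by construction, since a rounded change can only be 0.0 or 0.1 there, so it could be dropped.

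In either case, write the formula as -log10(m/M) for clarity. The cost is an edit to SAP wording and the table shell, with no new data.

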7.7. Pharmacokinetic Analysis

Plasma concentrations and PK parameters will be determined for encorafenib, its metabolite (LHY746) and binimetinib. PK summaries will be presented for treatment naïve participants, previously treated participants and for all participants combined (overall) in the PK set. C1D1 is defined as single dose (i.e., first dose) and C1D15 is defined as steady state.

7.7.1. Plasma Concentrations of Encorafenib, LHY746, and Binimetinib

Plasma concentrations of encorafenib, its metabolite (LHY746), and binimetinib will be quantified at the time points indicated in Table 8:

Table 8. Pharmacokinetic Blood Sampling Times

Schedule ¹	Study Visit	Timing of Sample	Allowed Window
Serial	C1D1	0.5 hours postdose	± 5 min
		1.5 hours postdose	± 5 min
		3 hours postdose	± 10 min
		6 hours postdose	± 20 min
	C1D15	Predose	-30 min
		0.5 hours postdose	± 5 min
		1.5 hours postdose	± 5 min
		3 hours postdose	± 10 min
		6 hours postdose	± 20 min
		C2D1	Predose
Sparse	C1D1	Predose	-30 min
	C2D1	Predose	-30 min
	C3D1	Predose	-30 min
	C4D1	Predose	-30 min
	C5D1	Predose	-30 min
	C6D1	Predose	-30 min

¹ Serial blood sampling in participants enrolled under Protocol Version 0 through 3.0; sparse blood sampling for all participants enrolled from Protocol Version 4.0 onwards.

Protocol Amendment 4 implemented a change to the PK sampling schedule. All participants enrolled under the original protocol and up to and including Protocol Amendment 3 were subjected to serial PK blood sampling; however, all participants enrolled under Protocol Amendment 4 and later versions were subjected to sparse PK sampling assessments only (see

Table 8). Since there is only one common time point between the serial and sparse PK sampling schedules, separate PK TLFs will be presented for each sampling schedule.

All plasma concentration values for each participant in the safety set will be included in the bioanalytical plasma concentration listings, and participants will be identified as being in the PK set, as applicable. Individual concentration records will be flagged for the affected visit if any of the following occur:

- a. Participant had vomiting within 4 hours following study drug administration on the day of PK sampling (C1D1 and C1D15) or at any time over the preceding 24 hours.
- b. Plasma levels were not considered to be at steady-state (i.e. dosing was not performed for at least 4 consecutive days prior to C1D15 or C2D1).
- c. Subject received a higher or lower dose compared to planned treatment.
- d. PK sampling time was outside the allowed window or the elapsed time was not calculable.

The plasma concentrations of encorafenib, its metabolite (LHY746), and binimetinib will be summarized for all nominal time points, including predose (trough) concentrations, using the following descriptive statistics: N (number of participants in the population), n (number of participants with non-missing values), m (number of non-zero concentrations), arithmetic mean, standard deviation, coefficient of variation (CV), geometric mean, geometric standard deviation, geometric CV, minimum, median and maximum. An individual concentration-time data point will be excluded from the calculation of summary statistics if any of the above flags [a-d] apply. Concentrations reported as below the limit of quantification (BLQ) will be set to zero for the calculation of arithmetic mean, standard deviation, CV, minimum, median and maximum. For the calculation of geometric mean and geometric CV, BLQ values will be replaced by $\frac{1}{2}$ LLOQ. All summary statistics below the limit of quantification will be presented as “< X.XX” where X.XX represents the lower limit of quantification.

Concentration data, PK parameters, summary statistics and statistical analyses values will be presented to 3 significant figures.

The geometric mean with standard deviation* plasma concentration-versus-time profiles will be presented graphically for each analyte using both linear and semi-logarithmic scales on C1D1 and C1D15 and for trough concentrations of Day 1 of Cycles 1 through 6.

* Note: \pm (Standard Deviation) in this context represents the standard deviation calculated on a log scale; therefore, geometric standard deviation would be used as a multiplicative factor:

$$+\text{Geometric Standard Deviation} = \exp^{\text{Mean}_{\ln} + \text{Standard Deviation}_{\ln}} = \exp^{\text{Mean}_{\ln}} * \exp^{\text{Standard Deviation}_{\ln}} = \text{Geometric Mean} * \text{Geometric Standard Deviation}.$$

$$-\text{Geometric Standard Deviation} = \exp^{\text{Mean}_{\ln} - \text{Standard Deviation}_{\ln}} = \exp^{\text{Mean}_{\ln}} / \exp^{\text{Standard Deviation}_{\ln}} = \text{Geometric Mean} / \text{Geometric Standard Deviation} .$$

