7.8. Pharmacokinetics

For patients enrolled under Protocol Versions 0 through 3, serial blood samples (~4 mL each) for plasma PK analysis of encorafenib, its metabolite (LHY746), and binimetinib will be collected as shown in Table 12.

For patients enrolled under Protocol Version 4 or later, blood samples (~4 mL each)for plasma concentration of encorafenib, its metabolite (LHY746), and binimetinib will be collected as shown in Table 13.

Complete instructions for sample processing, handling and shipment will be provided in the Laboratory Manual.

Study visits for PK sampling should be scheduled in the morning so that proper predose and postdose PK blood samples can be collected. On the PK visit days, the morning doses of encorafenib and binimetinib will be taken at the study site under observation by the Investigator or designee at approximately the same time, only after collecting the predose PK sample. Predose sampling information will include the date and exact time of the most recent previous dose of binimetinib and encorafenib (except Cycle 1 Day 1), including the dose amount taken. Postdose sampling information, only needed for days with postdose PK sampling (i.e., Cycle 1 Day 1 and Cycle 1 Day 15), will include the date and exact time of the morning dose, including the dose amount taken. Except for the Cycle 1 Day 1 PK samples, which have to be obtained on the scheduled day, other PK samples may be obtained ± 1 day from the scheduled date.

If vomiting occurs within 4 hours following study treatment administration on the day of PK sampling, no additional study treatment will be taken in an effort to replace the material that has been vomited and it is recommended that no more PK samples be taken after the emesis occurs. Any vomiting that occurs will be noted in the PK eCRF. Further doses will be administered with premedication with antiemetic medications and PK sampling will be performed after premedication with antiemetics.

In addition, exploratory analyses on remaining plasma samples may be performed using a validated or non-validated, semi-quantitative or qualitative liquid chromatography tandem mass spectrometry method, if deemed appropriate.

Table 12.Serial Pharmacokinetic Blood Sample Timing in Patients Enrolled under
Protocol Versions 0 through 3

| Study Visit | Timing of Sample |
|----------------|---|

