8.4.4. Pharmacokinetic Analyses

Plasma concentrations of encorafenib and its metabolite (LHY746), and binimetinib will be determined using validated bioanalytical methods. Plasma concentration-time profiles for encorafenib, LHY746 and binimetinib will be generated for only patients enrolled under Protocol Versions 0 through 3. Descriptive summaries for encorafenib, LHY746 and binimetinib concentrations will be presented. Trough plasma concentration-visit of encorafenib and LHY746 and binimetinib will be reported and summarized for all patients treated in this study.

PK parameters will be determined for all PK-evaluable patients enrolled under Protocol Versions 0 through 3 using noncompartmental methods using Phoenix WinNonlin Version 8.0 or higher (Pharsight, Mountain View, CA). PK parameter estimates will be presented, summarized, and reported. Details of the analyses will be included in the SAP.

After IRB/IEC approval of Protocol Version 4, PK parameters of encorafenib and LHY746 and binimetinib will be estimated using a population model-based approach. Relationships between PK of encorafenib/binimetinib and biomarkers, clinical response and/or safety will be conducted using post hoc exposure estimates (eg, C_{max}, AUC or C_{min}) from population PK modeling, if possible and appropriate. Measures of efficacy may include but are not limited to ORR and DOR by IRR. Selection of safety measures will be based on frequency of observations or by selection of safety measures of interest. Analyses will be described in a separate stand-alone modeling plan and a separate report will be produced.

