5.4. PK Analysis Set

The PK analysis set includes all participants in the SS who have at least 1 postdose PK blood collection after the first dose of study treatment with associated bioanalytical results. The PK analysis set will be used for summaries of PK data.

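### Two SAP pharmacokinetic rules do not fit the sparse sampling schedule: the steady-state exclusion stops at C2D1, and the PK set requires a postdose sample that sparse participants are never scheduled to give

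*SAP*

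**What the plan says.** **Schedules.** SAP Table 8 has two. Participants under Protocol Versions 0 to 3 have serial sampling on C1D1 and C1D15 and one predose sample at C2D1. The other is "sparse blood sampling for all participants enrolled from Protocol Version 4.0 onwards", and every sample in it is predose (C1D1 and C2D1 to C6D1). Protocol Table 13 and the Schedule of Activities agree.

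**Exclusions.** SAP 7.7.1 lists four flags, a to d. Flag b marks levels not at steady state and defines that as "dosing was not performed for at least 4 consecutive days prior to C1D15 or C2D1". I read this as a sample not preceded by four consecutive days of dosing. The consequence is explicit: "An individual concentration-time data point will be excluded from the calculation of summary statistics if any of the above flags [a-d] apply". The same section summarises concentrations at all nominal time points and plots them "for trough concentrations of Day 1 of Cycles 1 through 6".

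**Population.** SAP 5.4 admits to the PK set safety-set participants with "at least 1 postdose PK blood collection after the first dose of study treatment" and a bioanalytical result, and uses that set for PK summaries. Protocol Table 14 has the same requirement. Protocol 8.4.4 says that troughs "will be reported and summarized for all patients treated in this study".

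**The concern.** Both rules match the serial schedule and miss the sparse one.

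For flag b, one trough curve would join a C2D1 point from which recently interrupted patients have been removed to C3D1–C6D1 points from which they have not clearly been removed. A difference between C2D1 and later cycles could then come from the rule and not from the drug.

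Gaps at those visits are foreseeable. Protocol 6.6.1 allows up to 42 consecutive missed days before a drug is stopped for good, which is longer than a 28-day cycle. Appendices 2 and 3 include holds of up to 4 weeks.

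For the PK set, the question is whether participants enrolled from Version 4 belong to the population in which their own troughs are to be summarised. If the wording is left as it is, someone must decide that at programming time, when the data may already be visible.

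**Working it through.** **1. The SAP's own count.** SAP 7.7.1 says the two schedules share one time point. From Table 8:

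| | Serial | Sparse |
|---|---|---|
| C1D1 | 4 postdose | 1 predose |
| C1D15 | 1 predose, 4 postdose | none |
| C2D1 | 1 predose | 1 predose |
| C3D1–C6D1 | none | 4 predose |
| Total | 10 | 6 |

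The only common cell is C2D1 predose, so the count of 1 is reproduced.

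**2. Reach of flag b.** Take the samples at visits after C1D1 and ask whether the visit is one that flag b names.
- Serial: 5 (C1D15) + 1 (C2D1) = 6, all named, so 6 of 6.
- Sparse: 1 (C2D1) + 4 (C3D1–C6D1) = 5, and only C2D1 is named, so 1 of 5.

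The four uncovered visits are exactly those that exist only in the sparse schedule. Extending the flag to them gives 5 of 5.

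**3. Postdose samples available.** Serial: 4 + 4 = 8 per participant. Sparse: 0. Protocol 7.8 uses the word the same way: postdose sampling information is "only needed for days with postdose PK sampling (i.e., Cycle 1 Day 1 and Cycle 1 Day 15"), and those are the serial days.

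**4. How many people the literal PK set would leave out.** The planned number is at least 60 + 37 = 97, and no more than 107 are expected. The number on serial sampling is not fixed in the plan. The Version 4 rationale in protocol Appendix 9 mentions about 50 patients with serial samples, which I take as an assumption.
- 97 − 50 = 47, and 47/97 = 48%.
- 107 − 50 = 57, and 57/107 = 53%.
- With 60 serial and 97 in total: 37/97 = 38%. With 40 serial and 107 in total: 67/107 = 63%.

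**5. Fit with the rest of the plan.** SAP 7.7.1 promises separate PK tables, listings and figures for each schedule. Troughs at Cycles 3 to 6 can come only from sparse participants. A PK set without them would leave those outputs empty and would not meet the trough summary in protocol 8.4.4.

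**6. Size of the flag b effect.** It depends on how many C3D1–C6D1 troughs follow a recent gap and how far those troughs differ from steady state. The documents give neither. Even the direction is not settled for encorafenib: protocol 6.5.1.1 describes it as metabolised by CYP3A4 and potentially inducing that enzyme, so a trough soon after restart need not be lower.

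**The case against.** **Other flags may do the work.** SAP 7.6.1.1 records an interruption as a 0 mg dose. Flag c (a dose above or below plan) could be read to include that. Flag d (outside the window, or elapsed time not calculable) arguably catches a predose sample with no dose following it. For patients still off drug on the sampling day this has force, although the SAP does not say so. It does not clearly cover a patient who restarted the planned dose one to three days before the visit, because neither flag looks back. If flag c covered that patient, flag b would have little to do at C2D1 either.

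**The intent about the PK set is plain.** A C2D1 trough is drawn after the first dose, and the planned sparse outputs show that these participants are meant to be included. The sentence in protocol 7.8 concerns what sites record, not who is analysed. This stands as evidence of intent. But that reading makes the word *postdose* redundant beside the reference to the first dose, and it goes against the predose/postdose usage of both documents.

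**Other rules were adapted.** Noncompartmental parameters are limited to serial participants, and outputs are split by schedule. Flag a names C1D1 and C1D15, but its clause on the preceding 24 hours can reach later troughs. The mismatch is therefore in two rules, not in the PK section as a whole.

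**Stronger readings that do not hold.** A reader might infer that the trough means will fall by a calculable amount, by counting the retained troughs as below the limit of quantification. That models patients still off drug, whom flags c or d may already remove; nothing in the documents suggests such values after one to three days of planned dosing. A reader might also infer a false decline over cycles. A constant share of affected troughs at C3D1–C6D1 gives one step after C2D1, and a progressive decline would need interruptions to become more frequent by cycle, which is not shown. Finally, a reader might infer that the sparse cohort will be lost. That follows only from the literal wording; the evident intent makes it unlikely, and SAP 7.7.1 lists concentrations for every safety-set participant in any case.

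**Conclusion.** Both mismatches are in the current text. Flag b covers 1 of 5 sparse troughs after C1D1, against 6 of 6 serial samples, so troughs after a recent dosing gap are handled differently at C2D1 and at C3D1–C6D1. An artificial step after C2D1 is possible, and its size cannot be estimated from the documents.

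The PK set, read literally, excludes everyone enrolled from Version 4. That is about half the study if roughly 50 participants are serial (38% to 63% if 40 to 60 are), and it contradicts the planned sparse outputs and protocol 8.4.4.

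The stakes are small. PK is an exploratory objective, and the effect is confined to descriptive concentration summaries and plots. Noncompartmental parameters, the accumulation model and the line-of-therapy tests on those parameters use serial participants. Population PK has its own modelling plan. ORR is untouched. This is a worthwhile clarification, not a threat to the trial's conclusions.

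**What to change.** 1. In SAP 7.7.1, apply flag b at every trough visit of both schedules: C1D15 and C2D1 to C6D1.
2. In SAP 5.4, define the PK set as safety-set participants with at least one PK sample collected after the first dose, whether nominally predose or postdose, and with a bioanalytical result. The C1D1 predose sample would not count; a C2D1 or later trough would.
3. Align protocol Table 14. Protocol Section 8 lets the SAP modify statistical methods and requires an amendment only for major changes to the primary endpoint or its analysis. The change can therefore be listed in SAP Section 6 now and carried into the protocol when it is next amended.

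The cost is two wording changes and one alignment. No new data are needed: dosing records are on the eCRF, and protocol 7.8 already collects the time and amount of the previous dose with each predose sample after C1D1. Make the changes before database lock, so that the population and exclusions are not chosen after the concentrations have been seen.
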